9.4.3 Sensitivity and Supplementary Analyses for Secondary Efficacy Endpoints

Sensitivity analyses are not planned for secondary variables. If they are done, they will be done in the same manner as for the primary variable. That is, the secondary endpoint of responder status of 50% reduction from baseline in the frequency of monthly migraine days across Months 5 and 6 is derived from the primary variable monthly migraine days, a sensitivity analysis will use the same logistic model, as described in Section 9.4.2, after imputation of missing data for the underlying primary variable by the mLOCF rate-change method.

The same supplementary analysis of ANCOVA, described in Section 4.3.5 and Section 9.3.4, will be performed for secondary endpoints, except that the corresponding baseline covariate will be for the variable being analyzed.

9.5 Additional Efficacy Endpoints and Analyses

The other endpoints are listed in Section 3.3. Analysis of these variables will be performed at the nominal significance level, without adjusting for multiplicity. Hence,

results will be considered descriptive and potentially supportive of the results for the primary and secondary endpoints.

The comparisons of interest for each of the other endpoints will be the pairwise comparisons of each BOTOX dose (195 U and 155 U) versus placebo, with no statistical comparison between the BOTOX doses.

In general, though, for continuous and ordinal variables (e.g., headache days, acute headache medication days, [REDACTED], scale scores), the change from baseline analysis will be done with the same type of MMRM or ANCOVA analyses described in Section 9.3.3 and Section 9.3.4 for the primary efficacy endpoint, except that the baseline covariate will be for the variable being analyzed. For [REDACTED] which is recorded as change scores, baseline for [REDACTED] score will be used as a surrogate baseline covariate, to adjust for variation in response that is due to baseline differences between treatment groups.

In general, for responder variables (e.g., responder status of 75% or 100% reduction from baseline in the frequency of monthly migraine days, responder status of at least 5-grade improvement in total HIT-6 score), analysis of the responder status will be done with the same methods described in Section 9.4.2 for the secondary variable of 50% responder status.

For monthly migraine days across weeks, the change from baseline analysis will be done with the same type of MMRM or ANCOVA analyses described in Section 9.3.3 and Section 9.3.4 for the primary efficacy endpoint, except that the model will use weeks instead of months. The counts for a given week will be prorated to 28-day counts before calculating the change from baseline.

The decile responder status of t% (i.e., t is from 0 to 100 by tens) reduction from baseline in the frequency of monthly migraine days across Months 5 and 6, defined as a subject with at least a t% reduction from baseline in the 2-month average of monthly migraine days over Months 5 and 6, will be assessed for each individual.

Continuous responder curve for responder status in frequency of monthly migraine days across Months 5 and 6 will be presented by treatment group across Months 5 and 6, respectively. The plots will display cumulative proportion of subjects with decile t% reduction (y-axis), with error bars for 95% CI, versus responder status of reduction from 0% to 100% (x-axis).

The Kaplan Meier curves of time to event data (e.g., first day of 50% improvement during the preceding week) will be provided. The difference between treatments in the medians for time to event will be the main interest.

Plots of least squares mean of change from baseline and their standard errors for monthly migraine days, monthly headache days and monthly acute headache medication days from the MMRM will be presented by treatment group and 28-day period and primary time point across Months 5 and 6.

Plots of visit mean and standard errors for monthly migraine days, monthly headache days and monthly acute headache medication days will be presented by treatment group and 28-day period and primary time point across Months 5 and 6.

The plot of achievement of $\geq 50\%$ improvement (decrease) in monthly migraine days will be presented by treatment group and 28-day period and primary time point across Months 5 and 6.

9.5.1

The [REDACTED] is to be reported at Day 1, Week 4, Week 8, Week 12, Week 16, Week 20, Week 24, Week 28, Week 32, Week 36, Week 40, Week 44 and Week 48 visits. The [REDACTED] is a single item questionnaire used to measure the subject's [REDACTED] in relation to migraine symptoms overall at the time of administration of the measure. The [REDACTED] uses a 5-point rating scale with responses ranging from [REDACTED]. The [REDACTED] score ranges from 1 to 5, where lower score indicates a better condition.

The main summary will be a change from baseline score, potentially ranging from -4 to +4, best to worst. The scores will be summarized as an ordinal variable, using observed data, with the pairwise comparisons of each BOTOX dose (195 U and 155 U) versus placebo examined by the same type of ANCOVA analysis described in Section 9.3.4. The summary statistics will include response frequencies as well as distribution parameters.

9.5.2 [REDACTED]

The [REDACTED] is to be reported at Week 4, Week 8, Week 12, Week 16, Week 20, Week 24, Week 28, Week 32, Week 36, Week 40, Week 44 and Week 48 visits. The [REDACTED] is a single item used to measure the subject's [REDACTED] in migraine since the first dose of study intervention. The measure uses a 7-point rating scale with responses ranging from [REDACTED]. The [REDACTED] score ranges from 1 to 7, where 7 should indicate worsening and 1 should indicate improvement.

The main summary is that the [REDACTED] scores will be summarized as an ordinal variable, using observed data, with the pairwise comparisons of each BOTOX dose (195 U and 155 U) versus placebo examined by the same type of ANCOVA analysis described in Section 9.5. The summary statistics will include response frequencies as well as distribution parameters.

The second summary will collapse scores to a dichotomous responder status of participants with [REDACTED] score of "much better" or "very much better" across Months 5 and 6. The analysis of the responder status will be done with the same methods described for the secondary variable of 50% responder status (Details described in Section 9.4.2).

9.5.3 [REDACTED]

The [REDACTED] is to be reported at screening, Day 1, Week 12, Week 24, Week 36, and Week 48 visits. The [REDACTED] focuses on the 9 diagnostic criteria, with each question on a 0 (not at all) to 3 (nearly every day) scale. Subjects with a total score of 15 or greater at Visit 1 (or potentially confounding [REDACTED] per the investigator's discretion), are to be

excluded from study entry. The [REDACTED] can range from 0 to 27, the higher the score the more symptoms of [REDACTED] a subject experiences, and the more severe their [REDACTED]. Typical thresholds in the [REDACTED] scoring are as follows: 0 to 4 (none); 5 to 9 (mild); 10 to 14 (moderate); 15 to 19 (moderately severe); and ≥ 20 (severe).

The response is a change from baseline score. The scores will be summarized as an ordinal variable, using observed data, with the pairwise comparisons of each BOTOX dose (195 U and 155 U) versus placebo examined by the same type of ANCOVA analysis described in Section 9.3.4. The summary statistics will include response frequencies as well as distribution parameters.

9.5.4 [REDACTED]

The [REDACTED] is to be reported at Day 1, Week 12, Week 24, Week 36, and Week 48 visits. The [REDACTED] is a 5-item questionnaire designed to quantify [REDACTED] over a 3-month period. In this study, a modified version of the [REDACTED] will be utilized to shorten the recall period to 1 month. The [REDACTED] score is the sum of [REDACTED]

[REDACTED]
[REDACTED]
due to headaches and in the month prior to the assessment.

The baseline and change from baseline for the total [REDACTED] score will be summarized as a continuous variable, using observed data, with the pairwise comparisons of each BOTOX dose (195 U and 155 U) versus placebo examined with the same type of ANCOVA analysis described in Section 9.3.4.

9.5.5 [REDACTED]

The [REDACTED] is to be reported at Day 1, Week 4, Week 8, Week 12, Week 16, Week 20, Week 24, Week 28, Week 32, Week 36, Week 40, Week 44 and Week 48 visits. It will be used to assess [REDACTED]. The measure uses a 1-week recall and contains 6 questions related to [REDACTED]. The [REDACTED] measures

both [REDACTED]. The measure yields 4 scores, expressed as percentage of impairment, each ranging from 0% to 100%: [REDACTED]
[REDACTED]
[REDACTED].

For the [REDACTED] scores, each with ordered response categories, comparisons of the changes from baseline between treatment groups will be done with the same type of ANCOVA analysis described in Section 9.3.4.

9.5.6 [REDACTED]

There are 2 variables derived from [REDACTED], the [REDACTED] descriptive system and the [REDACTED]. The [REDACTED] is to be reported at Day 1, Week 12, Week 24, Week 36, and Week 48 visits.

- [REDACTED]
[REDACTED]
[REDACTED] The health state is a 5 digit number, with each digit being the problem level: Level 1 no problems, Level 2 slight problems, Level 3 moderate problems, Level 4 severe problems, and Level 5 extreme problems) for the 5 health state dimensions in order (digit 1 mobility, digit 2 self-care, digit 3 usual activities, digit 4 pain/discomfort, and digit 5 anxiety/ depression). For example, health state 11111 indicates no problem for any of the five dimensions, while health state 11235 indicates no problems with mobility or self-care, slight problems with performing usual activities, moderate pain or discomfort, and extreme anxiety and depression. The health state score will be calculated from the 5digit health state using the country-specific cross-walk value sets. For a country without a value set developed, another country-specific cross-walk set of values that most closely approximates that country will be used.
- [REDACTED] to indicate the subject's own health state, for baseline and changes from baseline.

The [REDACTED] will each be summarized for baseline and change from baseline. Summary statistics for each treatment for each visit window will be as described in Section 4.3.4. For changes from baseline, positive scores will indicate improvement for [REDACTED].

There is no plan to analyze the 5 dimensions of the [REDACTED] separately.

For the [REDACTED], treatment comparisons of baseline and the changes from baseline will be done with the same type of ANCOVA analysis described in Section 9.3.4.

9.5.7 Responder Analysis for Clinical Outcome Assessment Scores

Empirical cumulative distribution functions (eCDFs) are recommended as supportive analyses to inform the interpretation of meaningful treatment benefit for change from baseline endpoints based on clinical outcome assessments (COAs) included as primary and/or key secondary endpoints intended for approval and labeling.

To aid in the interpretation and contextualization of secondary endpoints constructed from COAs specifically, the MSQ v2.1 RFR domain score, and AIM-D PI domain score eCDFs of the change from baseline at Month 6 for the MSQ v2.1 RFR endpoint, and across Months 5 and 6 for the AIM-D PI endpoint will be plotted by treatment group. The eCDF curves for the MSQ v2.1 RFR and AIM-D PI will include all participants who meet all ITT population definition requirements and have an evaluable value at baseline and the specified outcome period. Change from baseline scores will be plotted on the horizontal axis and the cumulative percentage of subjects experiencing that specific level of change on the vertical axis.

eCDFs provide a visual display of the cumulative percentage of subjects within each group that achieve within-patient change across the entire distribution of change, thereby illustrating the percentage of responders across the range of potentially meaningful change threshold values. The following meaningful within-patient change (MWPC) responder thresholds will be utilized to develop the following responder endpoints:

[figure not shown]
1. MSQ v2.1 RFR responder at Month 6 using cutoff of █: Individual-level score change of \geq █ points can be considered clinically meaningful; (i.e., a participant whose MSQ v2.1 RFR domain score improves (increases) by \geq █ points from baseline at Month 6 can be considered a responder).³
2. MSQ v2.1 RFR responder at Month 6 using cutoff of █: Individual-level score change of \geq █ points can be considered clinically meaningful; (i.e., a participant whose MSQ v2.1 RFR domain score improves (increases) by \geq █ points from baseline at Month 6 can be considered a responder).⁴
3. AIM-D PI responder across Months 5 and 6 using the cutoff of █: Individual-level score change of \leq █ points can be considered clinically meaningful; (i.e., a participant whose PI domain score of the AIM-D improves (decreases) by \geq █ points from baseline across Months 5 and 6 can be considered a responder).³ This MWPC threshold for the AIM-D PI was corroborated through psychometric evaluation and score interpretation analyses using the Phase 3 data (M21307/PRECLUDE).

For the MSQ v2.1 RFR and AIM-D PI responder endpoints defined above, a raw summary of the proportion of responders will be provided and comparisons of each BOTOX dose (195 U and 155 U) versus placebo will be done using logistic regression using the same ANCOVA analysis model described for the primary variable (i.e., the MMRM model used for the primary analysis, but without repeat measures). The analysis model will include treatment (BOTOX 195 U, BOTOX 155 U, and placebo), country and strata of █ as fixed effects, with the corresponding baseline as a covariate, included as a continuous variable. The analysis will be performed based on postbaseline values at the specific timepoints. The treatment difference in terms of odds ratio between each BOTOX dose group and placebo will be estimated and tested from these models.

9.6 [REDACTED]

At the end of the double-blind phase of study (Week 24), in order to evaluate treatment [REDACTED], the participant will be asked to indicate which [REDACTED] [REDACTED]. This assessment will include 2 questions: (1) The [REDACTED], and (2) [REDACTED]

[figure not shown]
The [REDACTED] assessment asks the participant to indicate the response using the scale below that best describes the [REDACTED] assigned:

For data summary, responses to the Question (1) above will be summarized on a 5-point scale: [REDACTED]

[REDACTED] The response frequencies will be summarized with descriptive statistics, but inferential statistics will not be generated. Interpretation of the results should be done with awareness that [REDACTED] is confounded with efficacy and safety.

The second question asks the participant to indicate the reason(s) why they chose their response to Question (1):

Response option selected on above question will be populated with the response option selected by the participant on Question (1).

The subject [REDACTED] will be calculated and presented for each treatment group.

9.7 Efficacy Subgroup Analyses

The primary effectiveness analysis (MMRM of change in monthly migraine days without the fixed effect of the corresponding subgroup variable) will be repeated for subgroups defined by each randomization stratification subgroup (monthly migraine days at baseline \geq [REDACTED] [yes/no] and [REDACTED] [yes/no]), for medication overuse subgroup [yes/no] (see Section 8.2 in the Operations Manual), for each gender, for each country, age [$< 40, \geq 40$], for each race and for prior prophylactic treatment failure subgroup [failed fewer than [REDACTED] preventive treatments or failed at least [REDACTED] preventive treatments].

10.0 Safety Analyses

10.1 General Considerations

In general, adverse events (AEs) data will be analyzed and presented for

1. The double-blind phase (i.e., AEs with start date or increase in severity on or after Day 1 through the last day preceding the Week-24 injection).
2. The open-label phase (i.e., AEs with start date or increase in severity on or after the injection day of the Week-24 treatment through Week 48 visit). Subjects who complete the double-blind, placebo-controlled phase to enter the open-label phase will be included in this analysis.
3. The entire post-injection study duration (i.e., AEs with start date or increase in severity on or after Day 1 through Week 48 visit).
4. Each treatment cycle (i.e., AEs with start date or increase in severity on or after day of injection through last day preceding subsequent injection of study treatment).

In each of cases 1-4 above, a specific AE will only count once per subject, associated with its worst severity during the time period of interest. Unless stated otherwise, the method of analyses described in this section will be applied to each of the 4 cases.

Safety data will be summarized for the Safety Analysis Set. Safety summaries will be presented by treatment group. For the safety analysis, participants are assigned to a treatment group based on the treatment actually received, regardless of the treatment randomized.

The safety parameters will include adverse events (AEs), clinical laboratory test results (hematology, chemistry and urinalysis), vital signs, C-SSRS, and concomitant medications and procedures. For clinical laboratory and vital signs, the last non-missing safety assessment before the first dose will be used as the baseline for all analyses of that safety parameter. Continuous variables will be summarized by number of participants and mean, SD, median, Q1, Q3, minimum, and maximum values. Categorical variables will be summarized by number and percentage of participants.

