5.6 Follow-Up After Subject Discontinuation of Study Drug or from Study

To minimize missing data for efficacy and safety assessments, subjects who prematurely discontinue study drug treatment should continue to be followed for all regularly scheduled visits, unless subjects have decided to discontinue study participation entirely (withdrawal of informed consent). Subjects should be advised on the continued scientific importance of their data even if they discontinue treatment with study drug early.

If a subject prematurely discontinues study participation (withdrawal of informed consent), the procedures outlined for the exit/PD visit (Week 48/Visit 14) should be completed as soon as possible, preferably within 2 weeks. In addition, if subject is willing, a 30-day follow-up phone call after the last dose of study drug may be completed to ensure all treatment-emergent AEs (TEAEs)/SAEs have been resolved.

In the event a subject withdraws consent from the clinical study, biomarker research will continue unless the subject explicitly requests analysis to be stopped. When AbbVie is informed the patient has withdrawn and no longer wishes biomarker samples research to continue, samples will not be analyzed, and no new biomarker analysis data will be collected for the withdrawn subject or added to the existing

data or database(s). Data generated from biomarker research, before subject withdrawal of consent, will remain part of the study results.

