Important Medical Event Requiring Medical or Surgical Intervention to Prevent Serious Outcome	An important medical event that may not be immediately life-threatening or result in death or hospitalization, but based on medical judgment may jeopardize the subject and may require medical or surgical intervention to prevent any of the outcomes listed above (i.e., death of subject, life-threatening, hospitalization, prolongation of hospitalization, congenital anomaly, or persistent or significant disability/incapacity). Additionally, any elective or spontaneous abortion or stillbirth is considered an important medical event along with any suspected transmission of an infectious agent via a medicinal product if no other serious criterion is applicable. Examples of such events include allergic bronchospasm requiring intensive treatment in an emergency room or at home, blood dyscrasias or convulsions that do not result in inpatient hospitalization, or the development of drug dependency or drug abuse.

All AEs reported from the time of consent through the last study visit (i.e., 12 weeks after the last study drug administration) or through 30 days after the last study drug administration (for subjects who discontinue prematurely) will be collected, whether solicited or spontaneously reported by the subject. In addition, study procedure-related serious and nonserious AEs will be collected from the time the subject signs the study-specific informed consent.

The following definitions will be used for Serious Adverse Reactions (SAR) and Suspected Unexpected Serious Adverse Reaction (SUSAR):

SAR	Defined as all noxious and unintended responses to an IMP related to any dose administered that result in an SAE as defined above.
SUSAR	Refers to individual SAE case reports from clinical trials where a causal relationship between the SAE and the IMP was suspected by either the sponsor or the investigator, is unexpected (not listed in the applicable Reference Safety Information), and meets one of the above serious criteria.

AbbVie will be responsible for SUSAR reporting for the Investigational Medicinal Product (IMP) in accordance with global and local requirements.

All AEs will be monitored throughout the study to identify any of special interest that may indicate a trend or risk to subjects.

Adverse Events of Special Interest

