10.2.1 Treatment-Emergent Adverse Events

Adverse events will be coded by system organ class and preferred term using the Medical Dictionary for Regulatory Activities (MedDRA), version 23.0 or newer.

Any AEs that may occur before randomization will be listed but not summarized. Treatment-emergent adverse events (TEAEs) are defined as any AE began or worsened (increased in severity or became serious) on or after the first dose of study treatment and no later than the last dose of study treatment plus 30 days, or exit date, or death date within 30 days after exit visit, whichever occurs last. Events where the onset date is the same as the study treatment start date are assumed to be treatment-emergent. All treatment-emergent AEs will be summarized overall, as well as by primary MedDRA SOC and Preferred Term. The SOCs will be presented in alphabetical order, and the PTs will be presented in descending percentage within each SOC.

The number and percentage of subjects experiencing treatment-emergent AEs will be summarized.

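### The open-label and entire-study AE periods in SAP 10.1 stop at the Week 48 visit, short of the treatment-emergent window in SAP 10.2.1; the two ends should be aligned (minor)

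*SAP*

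**What the plan says.** SAP 10.1 sets four periods for AE tables. Case 1 is the double-blind phase, ending the day before the Week 24 injection. Case 2 is the open-label phase, covering AEs that start or worsen "on or after the injection day of the Week-24 treatment through Week 48 visit", in subjects who completed the double-blind phase and entered the open-label phase. Case 3 is the whole post-injection study: "AEs with start date or increase in severity on or after Day 1 through Week 48 visit". Case 4 is each treatment cycle: "on or after day of injection through last day preceding subsequent injection of study treatment". The section then says: "Unless stated otherwise, the method of analyses described in this section will be applied to each of the 4 cases".

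SAP 10.2.1 defines a treatment-emergent AE (TEAE) as one that begins or worsens from first dose and "no later than the last dose of study treatment plus 30 days, or exit date, or death date within 30 days after exit visit", taking whichever is last. It adds: "All treatment-emergent AEs will be summarized overall".

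For subjects who leave early, Protocol 5.6 says that "the procedures outlined for the exit/PD visit (Week 48/Visit 14) should be completed as soon as possible, preferably within 2 weeks". Protocol 6.1 says that their AEs "through 30 days after the last study drug administration (for subjects who discontinue prematurely) will be collected". For completers it collects AEs through the last study visit, 12 weeks after the last dose.

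The SAP version history (Section 14.0) records that version 3.0 extended the TEAE upper bound to bring in TEAEs leading to death. It logs no matching change to the periods in 10.1.

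**The concern.** Two current clauses give different end dates for the same tables. Section 10.2.1 decides which AEs are treatment-emergent, and Section 10.1 decides which of them reach each table. Where the first end is later than the second, an AE can be a TEAE by definition and still be missing from case 3, the only whole-study summary, and from case 2.

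This matters because SAP 2.1 makes long-term safety the objective of the open-label phase, and cases 2 and 3 are its incidence tables by system organ class and preferred term. The events at risk include those that version 3.0 extended the bound to capture. Depending on how the Week 48 visit is read, case 3 could also hold fewer events than case 1 for the same subject.

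**Working it through.** The plan has no figure to reproduce here, so the check is day arithmetic.

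**Inputs.** Last scheduled dose at Week 36 and last visit at Week 48 (Protocol 5.7 and 4.1); visit window ±3 days (Protocol 4.1); TEAE bound from SAP 10.2.1; period ends from SAP 10.1. Week w falls on Day 7w + 1.

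**Formula.** TEAE end = max(last dose + 30, exit, death date if within 30 days after exit). Shortfall = TEAE end minus the period end in 10.1.

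**Completers.**
- Week 36 = Day 253 and Week 48 = Day 337. The difference is 84 days, which matches the protocol's 12 weeks.
- Last dose + 30 = Day 283, which is 337 − 283 = 54 days before Week 48. With both visits at the unfavourable edge of their windows: (337 − 3) − (253 + 3 + 30) = 48 days. This leg never passes exit.
- The death leg can pass exit by up to 30 days, from Day 337 to Day 367. This is the only shortfall for completers, and it arises on either reading of the Week 48 visit.

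**Early exit, Week 48 visit read as the exit visit.** Protocol 5.6 supports this through its label, Week 48/Visit 14. For an exit k days after the last dose, with k < 30, the shortfall from the last-dose leg is 30 − k days:

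| k | Days outside the period |
|---|---|
| 7 | 23 |
| 14 | 16 |
| 28 | 2 |
| 30 or more | 0 |

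At k = 14 this is 16/30 = 53% of the 30 days. Which tables are affected depends on when the subject left:
- After the Day 1 or Week 12 injection, without entering the open-label phase: case 3 only, because the subject was never in case 2. Case 1 has no earlier stop for such a subject, so it could contain the event while case 3 does not.
- After the Week 24 or Week 36 injection: cases 2 and 3.

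**Early exit, Week 48 visit read as nominal Day 337.** Last dose + 30 is Day 31, 115, 199 or 283 for last doses at Day 1, Week 12, Week 24 or Week 36. All are before Day 337, so this leg loses nothing. The death leg passes Day 337 only for an exit after Day 337 − 30 = Day 307.

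**What is selected.** Cases 2 and 3 select on start date or increase in severity. A fatal AE that began before the period end stays in even if death came later. Only onset or worsening after the period end is lost.

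**The case against.** The strongest reply is that the gap is nearly empty and the SAP's intent is plain. Section 10.1 opens in general terms and yields where something else is stated. Section 10.2.1 then says that all TEAEs are summarized, and version 3.0 shows that fatal TEAEs were meant to be counted. Section 10.2.2 has a row for all deaths, Section 10.2.4 lists all deaths and all serious AEs, and Section 3.4 puts every AE in subject-level listings. Case 4 has no stated end for the last cycle, so it does not exclude these events.

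The early-exit part is also open to challenge. The SAP 4.2 visit windows count days since the latest injection, so a visit 14 days after an injection maps to Week 4, 16, 28 or 40, never to Week 48.

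Most of this stands, and it limits the point. It does not remove it. Section 10.2.1 defines which AEs are treatment-emergent and does not redefine the periods, so the intent has to be inferred. Listings do not give incidence by arm. The SAP does not say how cases 2 and 3 end for a subject who has no Week 48 visit.

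A reader might infer that the lost AEs are the ones that drove subjects out of the study. The documents do not support that: an AE that caused an exit began before it, so exit does not remove it from the tables for that subject's phases. A reader might also infer that treatment-emergent and fatal events after exit drop out of both tables as a class. That is too broad, for the reasons shown in the day arithmetic.

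**Conclusion.** The mismatch is real and minor. On either reading of the Week 48 visit, an AE that starts or worsens after a Week 48 exit and before a death within 30 days is a TEAE that cases 2 and 3 exclude. This partly defeats the version 3.0 extension. The early-exit loss exists only if the Week 48 visit means the exit visit, and the SAP leaves that open.

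The number of events cannot be computed, because the documents give neither the timing of early exits nor a death rate. It is probably very small. If one assumed that 0.5% to 2% of the 777 subjects exit within 30 days of an injection, that would be 777 × 0.005 = 3.9 to 777 × 0.02 = 15.5 subjects. That share is an assumption. It counts subjects with some shortfall rather than events, applies only on the exit-visit reading, and overstates case 2, which excludes double-blind dropouts.

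No efficacy result or error rate is touched, and the double-blind AE comparison in case 1 does not depend on the Week 48 end.

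**What to change.** In SAP 10.1, cases 2 and 3, replace the Week 48 visit as the end point with the end of the treatment-emergent period defined in Section 10.2.1. This also settles where the two periods end for a subject who has no Week 48 visit.

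The cost is one phrase and the matching programming flag. For early leavers no new data are needed in principle, since Protocol 6.1 already collects AEs to 30 days after the last dose, although Protocol 5.6 leaves the follow-up call to the subject's willingness. For deaths after a Week 48 exit, Protocol 6.1 does not routinely collect AEs past the last visit, so the change lets the tables include such records where they exist but does not guarantee that they do. It alters a tabulation window only and leaves clinical management as it is.
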